## Definition of 'all prior history'

All prior history will be defined as the SIB results obtained from the *lifetime* assessment at the first visit (Visit 1).

Worst case is defined by an answer 'yes' to the SIB category.

## Data summaries at the study level

SIB data will be summarized for the Safety Set. The number and percentage of subjects with suicidal ideation, suicidal behavior and self-injurious behavior without suicidal intent will be presented by analysis-period (all prior history and any time post-baseline) and treatment group. The following 14 events will be included in the summary table:

- Each of the 11 categories listed in Table 7-1, separately
- Any suicidal ideation or behavior (a 'yes' answer to at least one of the 10 suicidal ideation and behavior questions in analysis-period of interest)
- Any suicidal ideation (answered 'yes' to at least one of the 5 suicidal ideation questions in analysis-period of interest)

Protocol No. CFTY720D2312

 Any suicidal behavior (answered 'yes' to at least one of the 5 suicidal behavior questions in analysis-period of interest).

For those analyses, each subject can only be counted once for each event. However, a subject can be counted in several different events.

Suicidal ideation and behavior data will be listed. Detailed answers to C-SSRS items will be listed separately for subjects with any suicidal ideation at any time post-baseline (i.e. a 'yes' answer to at least one of the five suicidal ideation questions at any time post-baseline) and for subjects with any suicidal behavior at any time post-baseline (i.e. a 'yes' answer to at least one of the five suicidal behavior questions at any time post-baseline).

## 9 Interim analyses

No efficacy interim analyses are planned. On an as-needed basis, safety interim analysis for the DSMB will be performed by an independent statistician and independent statistical programmer. The analysis plan for these safety interim analyses will be provided in a separate document.

## 10 Determination of sample size

The study will randomize a total of 1960 patients, and is planned to provide approximately 90% power for the comparison of fingolimod 0.5 mg to glatiramer acetate at a 2-sided significance level of 0.05.

The sample size calculation is based on simulations from a negative binomial distribution with a constant dispersion parameter k.

The power of the study was evaluated under various ARR assumptions and various dropout patterns based on the cumulative literature on glatiramer acetate and the Novartis data on fingolimod. The basis of the assumptions for this study and their level of uncertainty are presented in Section 9.4.2 under the sub-header "Multiplicity adjustment for statistical hypothesis testing". The anticipated overdispersion parameter (k=0.2231) was observed in the Month-12 analysis of Study CFTY720D2301. The anticipated ARR for subjects treated with 0.5 mg fingolimod is  $\mu_{FTY~0.5~mg} = 0.195$ , the ARR for those treated with glatiramer acetate is  $\mu_{glatiramer~acetate} = 0.30$ . Therefore, the estimated ARR reduction for fingolimod 0.5 mg versus glatiramer acetate is 35%.

The total sample size of 1960 randomized is predetermined but the exact sample size of each arm will depend on when the randomization ratio switch occurs. For example, if the randomization ratio is switched when a total of 800 patients have been randomized from an original ratio of 1:1:1 for fingolimod 0.25 mg, fingolimod 0.5 mg, or glatiramer acetate, respectively to a ratio of 5:3:2, then 847 patients will be randomized to fingolimod 0.25 mg, 615 patients to fingolimod 0.5 mg and 498 patients glatiramer acetate, which will provide more than 90% power to demonstrate superiority of fingolimod 0.5 mg dose versus glatiramer acetate in terms of ARR at a 2-sided significance level of

0.05 assuming a 15% drop-out rate. The calculations take into account that patients who discontinue prematurely from the study can participate with partial data to the primary endpoint.

Fingolimod 0.25 mg has never been studied in a clinical trial in MS. Based on PK/PD modeling results, it is anticipated that the ARR in subjects treated with fingolimod 0.25 mg is approximately 15% higher than in those treated with fingolimod 0.5 mg. However, the uncertainty of this estimate is high; the 95% confidence interval of the estimated ARR in fingolimod 0.25 mg group ranges from 0.18 to 0.30. It is therefore anticipated that fingolimod 0.25 mg is less efficacious than fingolimod 0.5 mg, but more efficacious than glatiramer acetate. In line with the PK/PD modeling the anticipated ARR in subjects treated with fingolimod 0.25 mg is  $\mu_{\text{FTY 0.25 mg}} = 0.225$ , which corresponds to a reduction in ARR of 25% in subjects treated with fingolimod 0.25 mg compared to those treated with glatiramer acetate.

Following the multiplicity adjustment procedure in Multiplicity adjustment section 4.2.1.1, the power to detect a 25% reduction in ARR for subjects treated with fingolimod 0.25 mg compared with subjects treated with glatiramer acetate is approximately 68% at a 2-sided significance level of 0.05, if the primary objective for the fingolimod 0.5 mg dose can be rejected first; the corresponding marginal power with multiplicity adjustment is approximately 61%. If fingolimod 0.25 mg is similarly efficacious as fingolimod 0.5 mg (i.e., ARR reduction versus glatiramer acetate is 35% rather than 25%), the power to detect this treatment effect at a 2-sided significance level of 0.05 is approximately 88%. If fingolimod 0.25 mg is similarly efficacious as glatiramer acetate (i.e., estimated ARR in the fingolimod 0.25 mg group is at the high end of range proposed by the PK/PD model), there will be no significant difference at a 2-sided significance level of 0.05.

Due to the study early termination approved in December 2016 the final number of randomized patients is 1064 with 370 for fingolimod 0.25 mg, 352 for fingolimod 0.5 mg and 342 for glatiramer acetate. The statistical power based on the final sample size is approximately 71% for comparison of fingolimod 0.5 mg vs glactiramer acetate. For the comparison of fingolimod 0.25 vs glactiramer acetate the statistical power is approximately 44% without multiplicity adjustment and 31% with multiplicity adjustment.

The statistical software R (Version 2.13.1, open source) and the R library packages "MASS" and "PSCL" were used for sample size calculations and power analysis.

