Fingolimod 0.25 mg has never been studied in a clinical trial in MS. Based on PK/PD modeling results, it is anticipated that the ARR in patients treated with fingolimod 0.25 mg is approximately 15% higher than in those treated with fingolimod 0.5 mg. In line with the PK/PD modeling, the anticipated ARR in patients treated with fingolimod 0.25 mg is $\mu_{\text{FTY 0.25 mg}}$ =0.225, which corresponds to a 25% reduction in ARR in patients treated with fingolimod 0.25 mg compared to those treated with glatiramer acetate. Following the multiplicity adjustment procedure, the power to detect a 25% reduction in ARR for patients treated with fingolimod 0.25 mg compared with patients treated with glatiramer acetate is approximately 68% at a 2-sided significance level of 0.05, if the primary objective for the fingolimod 0.5-mg dose can be rejected first. A formal comparison between the two fingolimod doses is not intended, as the study is not powered for such a comparison.

The statistical software R (Version 2.13.1, open source) and the R library packages "MASS" and "PSCL" were used for sample size calculations and power analysis.

1 Introduction

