Fingolimod 0.25 mg has never been studied in a clinical trial in MS. Based on PK/PD modeling results, it is anticipated that the ARR in patients treated with fingolimod 0.25mg is approximately 15% higher than in those treated with fingolimod 0.5mg. However, the uncertainty of this estimate is high; the 95% confidence interval of the estimated ARR in fingolimod 0.25 mg group ranges from 0.18 to 0.30. It is therefore anticipated that fingolimod 0.25mg is less efficacious than fingolimod 0.5mg, but more efficacious than glatiramer acetate. In line with the PK/PD modeling the anticipated ARR in patients treated with fingolimod 0.25 mg is $\mu_{\text{FTY 0.25 mg}}$ =0.225, which corresponds to a reduction in ARR of 25% in patients treated with fingolimod 0.25 mg compared to those treated with glatiramer acetate.

Following the multiplicity adjustment procedure in Section 9.4.2, the power to detect a 25% reduction in ARR for patients treated with fingolimod 0.25 mg compared with patients treated with glatiramer acetate is approximately 68% at a 2-sided significance level of 0.05, if the primary objective for the fingolimod 0.5-mg dose can be rejected first. If fingolimod 0.25 mg is similarly efficacious as fingolimod 0.5 mg (i.e., ARR reduction versus glatiramer acetate is 35% rather than 25%), the power to detect this treatment effect at a 2-sided significance level of 0.05 is approximately 88%. If fingolimod 0.25 mg is similarly efficacious as glatiramer acetate (i.e., estimated ARR in the fingolimod 0.25-mg group is at the high end of range proposed by the PK/PD model), there will be no significant difference at a 2-sided significance level of 0.05.

The statistical software R (Version 2.13.1, open source) and the R library packages "MASS" and "PSCL" were used for sample size calculations and power analysis.

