## 12.1.1.1 Negative binomial regression model

The primary efficacy variable (aggregate ARR) will be analyzed using a negative binomial regression model. This analysis will be performed on the full analysis set and the per-protocol set. All 3 treatment groups will be used to fit the regression model in the analysis. In addition, the negative binomial regression model will be used for several supportive analyses for aggregate ARR and number of new or newly enlarged T2 lesions.

Negative binomial regression is used for modeling count variables, usually for overdispersed count outcome variables, while adjusting for one or more covariates. In general, Negative binomial regression analyzes the distributed data in the following form

$$Y_i \sim NB(r_i, p_i)$$
, for  $i = 1, \dots, n$ .

where the **negative binomial distribution** is a discrete probability distribution of the number of successes in a sequence of Bernoulli trials before a specified (non-random) number of failures (denoted r) occur with a probability p.

The log of the count variables are modeled as a linear function of the  $X_i$ .

$$\log(y_i) = \beta_0 + \beta_1 x_{1,i} + \dots + \beta_k x_{k,i}$$

Below is an example of the SAS codes used to perform the analysis of the negative binomial regression. The independent variables and covariates in the model may change per analysis defined in this document.

\*\*\*\*\*\*\*\*\*\*\*\*\*\*\*\*\*\*

```
* SAS Codes: Negative binomial regression model
* Variables in the model:
* relnum = number of relapses
* trt = treatment group code
* reg1a = region code
* n2 = number of relapses in previous year
* bledss = baseline EDSS
* sid1a = subject ID
* lnday = log(days in study/365.25)
*********************
proc genmod data=data1;
    class trt regla;
    model relnum=trt reg1a n2 bledss / dist=nb
                                      link=log
                                      offset=lnday maxiter=500 lognb;
    1smeans trt /cl;
    estimate 'A - B' trt 1 - 1 0/\exp;
    estimate 'A - C' trt 1 	 0 	 -1/\exp;
```

```
estimate 'B - C' trt 0 1 -1/exp;

ods output estimates=est;

ods output lsmeans=lst;

run;
```

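### SAP section 10: the final 31% gated power for fingolimod 0.25 mg equals an independence product; the SAP's own 71% and 44% imply about 37%, and the planned 68%, 61% and 88% need joint recomputation and labels

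*SAP*

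**What the plan says.** SAP section 4.2.1.1 tests 0.25 mg against GA only if 0.5 mg against GA is significant, each at two-sided 0.05. SAP section 12.1.1.1 uses one model for both contrasts: "All 3 treatment groups will be used to fit the regression model in the analysis".

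SAP section 10 then gives two sets of power figures.

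- **Final sample** (370 / 352 / 342 for 0.25 mg / 0.5 mg / GA): "The statistical power based on the final sample size is approximately 71% for comparison of fingolimod 0.5 mg vs glactiramer acetate". For 0.25 mg, "the statistical power is approximately 44% without multiplicity adjustment and 31% with multiplicity adjustment".
- **Planned sample** (847 / 615 / 498): about 90% for 0.5 mg in the opening sentence, and more than 90% where these arm sizes are given. For 0.25 mg it gives about 68%, "if the primary objective for the fingolimod 0.5 mg dose can be rejected first", and then "the corresponding marginal power with multiplicity adjustment is approximately 61" per cent. If 0.25 mg were as effective as 0.5 mg (35% reduction), the figure is 88%.

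The protocol synopsis and section 9.6 carry the same 68% with the same condition, "if the primary objective for the fingolimod 0.5-mg dose can be rejected first". Section 9.6 also has the 88%: "the power to detect this treatment effect at a 2-sided significance level of 0.05 is approximately 88" per cent. The 61% and 31% appear only in the SAP.

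Power was "evaluated under various ARR assumptions and various dropout patterns", by simulation. Neither the dropout timing nor the correlation between the tests is reported.

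**The concern.** Under the step-down rule, power for 0.25 mg with multiplicity adjustment is the probability of rejecting both hypotheses. Both contrasts subtract the same GA estimate. A trial in which the GA rate happens to be high favours both fingolimod doses, so the tests are positively correlated and the joint probability exceeds the product of the two separate powers. The stated 31% is nevertheless that product to the rounding shown.

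The planned 61% is also a product: 0.90 x 0.68 = 61.2%. That is valid if 68% is conditional on rejecting the first hypothesis and invalid if 68% is ungated.

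At stake is how the chance of success for the low dose is reported. Section 10 is where the SAP gives the shortened trial's power for this dose, and a reader weighing a non-significant 0.25 mg result would use it.

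**Working it through.** **Inputs.** From SAP section 10: k = 0.2231; ARR 0.30 (GA), 0.195 (0.5 mg) and 0.225 (0.25 mg); the arm sizes above; 15% dropout, with dropouts contributing partial data. Mean exposure t (years) is an assumption. With one-year completers it lies between 0.85 (dropouts contribute nothing) and 1.0. Uniform dropout gives 0.85 + 0.15 x 0.5 = 0.925.

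**Formulas.**
- Variance of an arm's log rate: V = (1/(ARR x t) + k)/n.
- SE of a contrast: square root of V(dose) + V(GA).
- Ungated power: Phi(|log rate ratio|/SE - 1.96).
- Correlation of the two contrasts: V(GA)/(SE1 x SE2).
- Gated power: bivariate normal probability that both tests reject.

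**1. The stated figures as products.** 0.71 x 0.44 = 31.2% (stated 31%). 0.90 x 0.68 = 61.2% (stated 61%).

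**2. Final design, worked at t = 0.89.**
- V(GA) = (1/(0.30 x 0.89) + 0.2231)/342 = 0.01160. V(0.5 mg) = 0.01700. V(0.25 mg) = 0.01410.
- SE1 = 0.1691 and SE2 = 0.1603.
- 0.5 mg: Phi(0.4308/0.1691 - 1.96) = 72.1% (stated 71%).
- 0.25 mg ungated: Phi(0.2877/0.1603 - 1.96) = 43.4% (stated 44%).
- Correlation = 0.01160/(0.1691 x 0.1603) = 0.428.
- Joint power 37.0%; product 31.3%.

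The two separate powers reproduce. The gated one reproduces only as the product.

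**3. Directly from the SAP's 71% and 44%.** With correlation 0.428 the joint power is 37.0% (36.5-37.6% over rounding of the two inputs). Simulated Wald statistics correlate at about 0.52, which gives about 38%.

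**4. Sensitivity of the final figure to exposure.**

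| t | 0.5 mg | 0.25 mg ungated | product | joint |
|---|---|---|---|---|
| 0.85 | 70.3% | 41.9% | 29.4% | 35.2% |
| 0.89 | 72.1% | 43.4% | 31.3% | 37.0% |
| 0.925 | 73.7% | 44.7% | 33.0% | 38.5% |
| 1.0 | 76.8% | 47.5% | 36.5% | 41.7% |

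If every dropout contributes no follow-up at all, which contradicts the use of partial data, the joint power is still 34.9%.

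**5. Planned design: three readings of 68%.**

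| Reading of 68% | t that fits | 0.5 mg | ungated | conditional | joint |
|---|---|---|---|---|---|
| Ungated | 0.892 | 90.0% | 67.8% | 71.8% | 64.6% |
| Conditional | 0.789 | 86.4% | 62.8% | 68.0% | 58.7% |
| Already gated | 0.957 | 91.8% | 70.7% | 74.1% | 68.0% |

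- *Ungated:* gated power is about 65%, not 61%.
- *Conditional:* 61% would follow by valid multiplication, but the exposure needed is below the 0.85 floor and 0.5 mg power is below the stated 90%. If all dropouts contribute nothing, conditional power is 70.0%, gated power 61.9% and 0.5 mg power 88.4%.
- *Already gated:* the stated 61% is then wrong, because gated power is 68%.

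**6. The 88%** (35% effect for 0.25 mg). At t = 0.892, gated power is 86.2% and ungated 94.0%. At t = 0.957, gated power is 88.7%.

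**The case against.** There is no good defence of 31%. The 44% is labelled as unadjusted, so it cannot be conditional, and a shared control rules out a correlation near zero. What can fairly be said is that 37% is not exact: it moves with exposure and with the correlation used, so a range belongs beside it.

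The planned figures are different. A reader might infer that 68% is simply ungated, that 61% should become 65%, and that both documents should be relabelled to match. The documents do not support going that far. The 68% sentence opens by invoking the multiplicity procedure, so 68% may already be gated. At a mean exposure of 0.957 year that reading fits more than 90% for 0.5 mg, 68% and roughly 88% together, whereas the ungated reading at 0.892 leaves 88% unexplained. Against this, the SAP sets 61% beside 68% as the adjusted figure, and the final 71% and 44% point to lower exposure (at 0.95, the final 0.5 mg power would be 74.8%). The conditional reading misses by little at its extreme: 70.0% conditional and 61.9% gated, against figures given only as approximate. With the simulations unseen, prescribing a label or value could add an error.

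A reader might also infer that the error reaches the analysis. It does not. No alpha level, test or sample size depends on 31% or 61%, and randomisation had already closed at 1064 patients.

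**Conclusion.** The final 31% is wrong as written. The SAP's own 71% and 44% imply a gated power of about 37%, so the figure is about 6 points too low. Over mean exposure of 0.85-1.0 year the joint power is about 35-42%. This rests on the normal approximation, the stated ARRs and k, and an assumed exposure. The conclusion does not depend on the exposure chosen, because no value in that range gives less than 35%. That the sponsor multiplied the two powers is inferred from the match; no derivation is shown.

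For the planned sample the finding is narrower: the stated inputs do not reproduce 68% and 61% together with at least 90% for 0.5 mg under any of the three readings. Which figure is at fault cannot be settled from the documents.

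Severity is minor. Only reported power is affected, and 0.25 mg is underpowered at 31% or 37%.

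**What to change.** - **SAP section 10, final figures:** replace 31% with the jointly computed power (about 37%; roughly 35-42% depending on dropout timing) and state the dropout-timing assumption.
- **SAP section 10, planned figures:** recompute the gated power for 0.25 mg as a joint probability from the sponsor's three-arm simulations, and label 68%, 61% and 88% as ungated, conditional or joint. No value or label is proposed here.
- **Protocol:** give 68% and 88% matching wording in section 9.6, and 68% in the synopsis, at the next revision. Alternatively, record the difference in SAP section 11.

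The cost is one SAP paragraph, a rerun or relabelling of existing simulations, and a few words in the protocol or one line in SAP section 11. Design, testing order, alpha and sample size stay as they are.

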## 11 Documentation of changes from the protocol

# 12 Clinical Study Report Appendix 16.1.9 Documentation of statistical methods

## 12.1 Statistical methods and analysis outputs

## 12.1.1 Statistical methods

Statistical Analysis System (SAS) version 9.2 or higher will be used to perform all the statistical analyses in the report.

Pair-wise treatment comparisons will be performed using separated data for treatment groups (A vs. C, B vs. C, and A vs. B) for the following analyses: rank ANCOVA/ANOVA, survival analyses, Wilcoxon rank-sum test, and Fisher's exact test. Data from all treatment groups (A, B, and C) will be used for the following analyses: negative binomial regression, logistic regression, and ANCOVA.

## 12.1.1.1 Negative binomial regression model

The primary efficacy variable (aggregate ARR) will be analyzed using a negative binomial regression model. This analysis will be performed on the full analysis set and the per-protocol set. All 3 treatment groups will be used to fit the regression model in the analysis. In addition, the negative binomial regression model will be used for several supportive analyses for aggregate ARR and number of new or newly enlarged T2 lesions.

Negative binomial regression is used for modeling count variables, usually for overdispersed count outcome variables, while adjusting for one or more covariates. In general, Negative binomial regression analyzes the distributed data in the following form

$$Y_i \sim NB(r_i, p_i)$$
, for  $i = 1, \dots, n$ .

where the **negative binomial distribution** is a discrete probability distribution of the number of successes in a sequence of Bernoulli trials before a specified (non-random) number of failures (denoted r) occur with a probability p.

The log of the count variables are modeled as a linear function of the  $X_i$ .

$$\log(y_i) = \beta_0 + \beta_1 x_{1,i} + \dots + \beta_k x_{k,i}$$

Below is an example of the SAS codes used to perform the analysis of the negative binomial regression. The independent variables and covariates in the model may change per analysis defined in this document.

\*\*\*\*\*\*\*\*\*\*\*\*\*\*\*\*\*\*

```
* SAS Codes: Negative binomial regression model
* Variables in the model:
* relnum = number of relapses
* trt = treatment group code
* reg1a = region code
* n2 = number of relapses in previous year
* bledss = baseline EDSS
* sid1a = subject ID
* lnday = log(days in study/365.25)
*********************
proc genmod data=data1;
    class trt regla;
    model relnum=trt reg1a n2 bledss / dist=nb
                                      link=log
                                      offset=lnday maxiter=500 lognb;
    1smeans trt /cl;
    estimate 'A - B' trt 1 - 1 0/\exp;
    estimate 'A - C' trt 1 	 0 	 -1/\exp;
```

```
estimate 'B - C' trt 0 1 -1/exp;

ods output estimates=est;

ods output lsmeans=lst;

run;
```

## 12.1.1.2 Rank Analysis of Covariance (ANCOVA) and Rank Analysis of Variance (ANOVA)

Rank Analysis of Covariance (ANCOVA)

The supportive efficacy variable, subject-level ARR (confirmed relapse only), will be analyzed using the rank ANCOVA. Other secondary efficacy variables, subject-level ARR (confirmed and unconfirmed relapse), change from baseline in MRI variables, will be analyzed similarly on the full analysis set.

The rank ANCOVA is a non-parametric statistical method described in Stokes, Davis, and Koch (2000). It can be considered as an extension to the Wilcoxon rank-sum test with the ability to adjust for covariates in the model.

The analysis can be easily implemented using SAS by the following three steps:

- 1) compute the ranks of the response variable and covariate in the combined group of treatment using PROC RANK;
- 2) calculate the residuals from the linear regression of the response variable ranks vs. ranks of the covariates (without treatment) using PROC REG;
- 3) use the CMH mean score statistics to compare the mean values of the residuals in treatment by using TABLE scores (default scores) in PROC FREQ.

Below is an example of the SAS codes used to perform this rank ANCOVA. The independent variables and covariates in the model may change per analysis defined in this document.

\*\*\*\*\*\*\*\*\*\*\*\*\*\*\*\*\*\*\*

```
* SAS Codes: Rank ANCOVA model

* Variables in the model:

* relann = subject-level annualized relapse rates

* trt = treatment group code

* regla = region code

* n2 = number of relapses in previous year

* bledss = baseline EDSS
```

Protocol No. CFTY720D2312

```
* other covariates as well
* sid1a = subject ID
*******************
Data eff:
    Set eff;
    If regla=' ' or n2=. or bledss=. or relann=.then delete;
run;
proc rank data=eff nplus1 ties=mean out=ranks;
    by regla;
    var n2 bledss relann more convariates...;
run;
proc reg data=ranks noprint;
    by regla;
    model relann=n2 bledss more convariates...;
    output out=residual r=resid;
run;
proc freq data=residual;
    tables regla*trt*resid / noprint cmh2;
    where trt in ('A','B');
    output out=rancova cmh2;
    *** SELECT P CMHRMS;
run;
```

